6.1.2 Administration of the investigational medicinal products

Only patients enrolled in the study will receive the study products and only trained and authorised site staff will handle and supply them. Patients will receive the IMPs kit directly from the investigator or the medicine will be sent directly to the patient from the site pharmacy.

The patients will receive the IMP at baseline visit (V0: 2 bottles), V2 (2 bottles) and V3 (2 bottles) visits. They will be instructed to take the IMP orally twice a day (morning and evening uptakes). Intervals for dosing should ideally be about 12 hours (\pm 1 hour). Tablets shall be swallowed with a glass of water 30 minutes before the meal, in fasting condition. For patients who have swallowing difficulties, tablets can be taken in a spoon filled with jellified water. IFB-088 and riluzole will be taken at the same time. Dosage modifications are not permitted. However, in case of unplanned dosage modification by the patient, it shall be documented in the eCRF. Missed doses will not be made up for. In case of vomiting shortly after ingestion of the study product, the patient will leave out the potential missed dose and will take the next dose as normal. Study product doses withheld due to toxicities and AEs will not be made up later. Should the patient or the investigator wish to discontinue treatment for any reason, they may do so at any time. The date of the last uptake will be documented in the eCRF.

6.1.3 Supply and storage conditions of the investigational medicinal products

IFB-088 and placebo supplied by the sponsor to be used in this study will be manufactured, tested, handled and stored according to current Good Manufacturing Practice (GMP) requirements for clinical trials.

The sponsor will provide the study centre with the test product and the placebo. The investigator or pharmacist (if applicable) will receive numbered products. The investigator/pharmacist is responsible for a safe and proper handling and storage of the study drug at the investigational site. The study drug must be stored in a locked facility with restricted access to the investigator/pharmacist and authorised personnel. The study products have to be stored at room

temperature. The investigator or designee must confirm appropriate temperature conditions have been maintained during transit for each study product received.

The investigator and/or a pharmacist or another appropriately trained individual is obliged to document the receipt, dispensation, and return of all study products received during this study.

Records on receipt, use, return, loss, or other disposition of study drugs must be maintained. The investigator and/or a pharmacist or another appropriately trained individual must sign the receipt forms. Records on study drug delivery to the site, the inventory at the site, the use by each patient, and the return to the sponsor must be maintained by the investigator and/or a pharmacist or another appropriately trained individual at the investigational site. Patients will be asked to return all unused study drug and packaging at each visit, and at the time of study drug discontinuation. The following information will be recorded in the patient's file: dates, quantities, batch numbers, and the unique code numbers assigned to the study products and the patients. The investigators must maintain records documenting that the patients were provided with their respective doses specified in the protocol. Furthermore, they should reconcile all study drugs received from the sponsor. It is the responsibility of the investigator to give reasons for any discrepancies in IMPs accountability

All remaining IMPs, used and unused, shall be collected and returned to the sponsor for destruction at the end of the study.

6.1.4 Packaging and labelling of the investigational medicinal products

The study products will be packaged and labelled according to current GMP guidelines, good clinical practice (GCP) guidelines, and national legal requirements and instruction will be given in local language. KLS will be responsible for label compliance. Eurofins Gent will be responsible for the packaging, and Eurofins St Gely will be responsible for the labelling and shipping of the IMP and placebo to the investigating sites.

IFB-088 and placebo tablets are packaged in 40 mL high-density polyethylene bottles with polypropylene screw cap lids that contain desiccant. Each bottle contains 65 tablets covering the needs for a bi-daily administration over one month.

As *in vitro* data suggest that CYP1A2 is also the main isoenzyme involved in the metabolism of riluzole, and according to section 4.5 of riluzole SmPC, it should be noted that inhibitors of CYP1A2 (e.g. caffeine, diclofenac, diazepam, nicergoline, clomipramine, imipramine, fluvoxamine, phenacetin, theophylline, amitriptyline and quinolones) could potentially decrease the rate of riluzole elimination, while inducers of CYP1A2 (e.g. cigarette smoke, charcoal-broiled food, rifampicin and omeprazole) could increase the rate of riluzole elimination.

6.3 USE OF CONCOMITANT MEDICATIONS

Any medication, investigational agent, or vaccine, including over the counter or prescription medicines, vitamins, and/or herbal supplements, or other specific categories of interest that the participant is receiving at the time of enrolment or receives during the study must be recorded along with:

- Reason of use,
- Dates of administration including start and end dates,

- Dosage information including dose and frequency for concomitant therapy of special interest.

Other concomitant medication may be considered on a case-by-case basis by the investigator in consultation with the sponsor if required. The sponsor should be contacted if there are any questions regarding concomitant or prior therapy. Patients must be informed by the investigators about the fact that they may not take any drug, food supplement, vitamins, etc. on their own without the agreement of their referent investigator.

6.4 COMPLIANCE

Patient compliance with study medication will be assessed at each visit and at the time of study products discontinuation by the investigator by direct questioning and by recollection of IMP packaging. Patients will be asked to return all unused study products.

If the time for one visit exceeds the time window, this will be recorded as a deviation from the protocol. Any deviation from the prescribed dosage regimen is to be recorded in the eCRF.

7. ADVERSE EVENTS

7.1 DEFINITION OF AN ADVERSE EVENT

According to international conference on harmonisation (ICH), an AE is any untoward medical occurrence in a patient or clinical investigation subject administered a pharmaceutical product and which does not necessarily have a causal relationship with this treatment. An AE can therefore be any unfavourable and unintended sign (including an abnormal laboratory finding), symptom or disease temporally associated with the use of a medicinal (investigational) product, whether or not related to the medicinal (investigational) product. A clinically relevant worsening of a pre-existing condition during the study must also be recorded as an AE.

7.2 DEFINITION OF A TREATMENT EMERGENT ADVERSE EVENT

A TEAE is defined as any AE not present prior to the initiation of the treatments (that is before baseline visit: V0) or any event already present that worsens in either intensity or frequency following exposure to the treatments. AEs occurring after subject enrolment (ICF signature) but prior to first study drug administration will be recorded as a non-treatment emergent adverse event (NTEAE).

7.3 DEFINITION OF A SERIOUS ADVERSE EVENT

A SAE is defined as any untoward medical occurrence that:

- Results in death,
- Is life-threatening (the term 'life-threatening' refers to an event in which the patient was at risk of death at the time of the event; it does not refer to an event that hypothetically might have caused death if it was more severe),
- Requires in-patient hospitalisation or prolongation of existing hospitalisation,
- Results in persistent or significant disability or incapacity,

- Is a congenital anomaly or birth defect.

Medical and scientific judgement should be exercised in deciding whether expedited reporting is appropriate in other situations, such as important medical events that might not be immediately life threatening or result in death or hospitalisation but might jeopardise the patient or might require intervention to prevent one of the other outcomes listed above.

7.4 DEFINITION OF AN ADVERSE EVENT OF SPECIAL INTEREST

An AESI (serious or non-serious) is an AE of scientific and medical concern specific to the sponsor's product or program, for which ongoing monitoring and rapid communication by the investigator to the sponsor can be appropriate.

The following will be considered as AESIs:

- Renal toxicities,
- Symptomatic hypotension grade 2 (requiring non-urgent medical intervention) or above according to common terminology criteria for adverse events (CTCAE) version 5.0,
- Hypertriglyceridaemia (HTG). A cut-off value is set at triglycerides > 5.7 mmol/L (5.0 g/L) with at least 20% increase compared to baseline value.

7.5 DEFINITION OF A NEW FACT

New information which might alter the current benefit-risk assessment of the IMP or the trial; modify the use of the IMP, the conduct of the study, or documents related to the trial; or suspend, modify or terminate the clinical trial.

7.6 DEFINITION OF SUSPECTED UNEXPECTED SERIOUS ADVERSE REACTION

SUSAR is the term used to refer to an adverse event that occurs in a clinical trial subject, which is assessed by the sponsor and or study investigator as being unexpected, serious and as having a reasonable possibility of a causal relationship with the study drug.

7.7 RECORDING OF AN ADVERSE EVENT

The investigator must record all AEs presented or reported by the patient in the AE section of the eCRF. The start date, the actions taken (corrective treatments, dose decrease, temporary or definitive discontinuation of study product, premature withdrawal from the study, none, other) and the outcome (ongoing, recovered with/without sequelae, death) must all be recorded, and the investigator must assess the event in terms of seriousness, severity and relationship to the study products.

When possible, signs and symptoms should be reported as a diagnosis i.e. the investigator should avoid reporting only the signs and symptoms. If there is no medical diagnosis and the signs and symptoms have to be reported, the investigator should record a separate AE for each sign and symptom.

The severity of the AEs will be judged by the investigator(s) and recorded as follows:

- Mild: discomfort noticed but no disruption of normal daily activity,

- Moderate: discomfort sufficient to reduce or affect daily activity,
- Severe: inability to work or perform normal daily activity.

The relationship of the AE to the study product will be judged by the investigator(s) and recorded as follows:

- Not related: a reaction for which sufficient information exists to indicate that the aetiology is unrelated to the study drug; the subject did not receive the study medication or the temporal sequence of the AE onset relative to administration of the study medication is not reasonable or the event is clearly related to other factors (subject's clinical state, therapeutic intervention or concomitant therapy),
- Unlikely: Does not follow a reasonable temporal sequence from administration of the IMP, or is most likely related to another aetiology than the trial drug such as the patient's clinical state, environmental factors or other therapies,
- Possibly: a clinical event, including laboratory test abnormality, with a reasonable time sequence to administration of the drug but which could also be explained by concurrent disease or other drugs or chemicals,
- Probably: a clinical event including laboratory test abnormality, with a reasonable time sequence to administration of the drug, unlikely to be attributed to concurrent disease or other drugs and which follows a clinically reasonable response on withdrawal (de-challenge),
- Definitely: a reaction that follows a reasonable temporal sequence from administration of the drug, or in which the drug level has been established in body fluids or tissues, that follows a known or expected response pattern to the suspected drug, and that is confirmed by improvement on stopping or reducing the dosage of the drug, and reappearance of the reaction on repeated exposure (re-challenge if applicable).

For safety reporting purpose by the sponsor:

- Reasonable possibility: possibly, probably, definitely related AEs,
- No reasonable possibility: not related, unlikely related AEs.

All AEs and SAEs will be collected from the time of signing of the ICF until participation in study has ended. There is no time limit for investigators for reporting to the sponsor related SAEs they are made aware of.

Adverse events that begin before the start of study intervention but after signing of the ICF will be recorded on the AE eCRF (NTEAEs).

7.8 REPORTING OF SERIOUS ADVERSE EVENTS AND NEW FACTS

The investigator will immediately, i.e. within 24 hours from first knowledge, report, by fax or e-mail, any SAE occurring during the study to the safety officer (SO) acting on behalf of the sponsor of the study:

STRAGEN SERVICES S.A.S, [name]
[contact]
Email: [contact]

SAEs must be reported using the supplied SAE/AESI/pregnancy form. The investigator will complete in English and sign an SAE report form and transmit it to the SO by email or telefax not later than 24 hours after the first knowledge of the SAE. The SO acknowledges the receipt of the SAE information by email to the investigational site within one working day. In the absence of email acknowledging the receipt or in case of issue in sending the fax or email, the investigator shall contact the SO by any means for ensuring the receipt of SAE information at the earliest opportunity.

Although all AEs after signing the ICF are recorded in the eCRF, SAEs reporting to sponsor begins after the participant has signed the ICF and has received study intervention. However, if an SAE occurs after signing the ICF, but prior to receiving study intervention, it needs to be reported within the SAE reporting timeframe if it is considered reasonably possibly related to study procedures.

Details of all pregnancies in female participants will be collected for 90 days after end of treatment (V4). If a pregnancy is reported, the investigator should inform the sponsor within 24 hours of learning of the pregnancy, using the SAE/AESI/pregnancy form. The sponsor (via Stragen Services) will then follow up on such pregnancy with the investigator, using a dedicated pregnancy form, at least until pregnancy outcome. Abnormal pregnancy outcomes, for example, spontaneous abortion, foetal death, stillbirth, congenital anomalies, and ectopic pregnancy, are considered SAEs.

New facts which may impact the risk-benefit for enrolled patients and/or impact on the study conduct may not necessarily fulfil the definition and/or criteria for constituting an SAE. However, such information shall be provided to the sponsor in accordance with the process described for SAEs, i.e. within 24h from knowledge and using the SAE/AESI/pregnancy form.

Any FU information will be reported to the SO and to the sponsor as soon as it becomes known, with the same process and timelines as described here above for initial reports. The sponsor will ensure that all relevant information about SAE and SUSAR is recorded and reported to the national competent authorities (CAs) in all member states concerned and to IECs within the applicable regulation and local specificities.

SAEs occurring after the last study visit will only be reported if the investigator believes that the event may have been caused by the IMP or a protocol procedure.

Hospitalisation for a diagnosis or therapeutic procedure planned before study enrolment but performed after the enrolment should not be considered for SAE and should be reported in eCRF in concomitant procedures page.

7.9 REPORTING OF ADVERSE EVENTS OF SPECIAL INTEREST

AESIs should be reported via the same process established for SAEs, regardless of seriousness. AESIs, both serious and non-serious, must be reported within 24h from knowledge using the SAE/AESI form. The form will be named SAE/AESI/pregnancy form, as it is also used for the initial notification of pregnancy.

7.10 CLINICAL EVENTS RELATED TO ALS

Clinical events related to ALS or consisting in known ALS complications will be recorded in the AE section of the eCRF. When serious, these clinical events are exempt from SAE reporting, unless the investigator deems the event to be related to the administration of the study drug, or unless the event results in patient's death: in these 2 cases, the event should be reported as SAE. The following events will be considered clinical events related to ALS or ALS complications:

- Onset, changes or aggravation of speech and/or voice disorders,
- Onset, changes or aggravation of swallowing disorders including drooling, aspiration/choking,
- Onset, changes or aggravation of emotional disorders, including exaggerated and/or involuntary emotional responses, alteration and/or lack of control in emotive expression, fronto-temporal executive dysfunction,
- Onset, changes or aggravation of breathing difficulties,
- Onset, changes or aggravation of muscle and/or joint disorders and their consequences, including muscle weakness, muscle atrophy/wasting, muscle spasticity, muscle cramps, fasciculations, stiffness, joint pain and/or contractures, reduced dexterity, wrist drop, tripping, stumbling, awkwardness, foot drop, spasms, uncontrolled movements,
- Onset, changes or aggravation of upper and/or lower motor neuron signs and symptoms, including reflexes disorders (abnormal reflexes, hypo/hyperreflexia), abnormal motor nerve conduction studies.

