2. STUDY OBJECTIVES AND ENDPOINTS

Objectives	Endpoints
Primary	
To assess the safety of the test product, IFB-088 50 mg/day, in patients with bulbar-onset ALS.	
 Incidence, grade and relationship to IFB-088 for treatment emergent AEs, SAEs, and AESIs, AEs leading to dose interruption or premature discontinuation.
Secondary and exploratory	
 Change in ALSFRS-R score from baseline to month 3 and to month 6, Worsening according to ALS-MITOS score, i.e. progression to a higher stage at 3 and at 6 months compared to the baseline, Change in King's College score from baseline to month 3 and to month 6. 
Exploratory endpoints:
 
 Assessment of respiratory function (slow vital capacity [SVC], sniff test [optional], arterial blood gases [ABG]). Evaluation of nutritional status and body composition by bioelectrical impedance.
To determine the PK parameters of IFB-088.	
Measurements of PK parameters:
 
 Plasma concentration of IFB-088 and IFB-139, AUC of IFB-088 and IFB-139, Maximum observed plasma concentration (C_{max}), with associated T_{max}, Terminal or apparent terminal half-life ($t_{1/2}$), Apparent systemic clearance, apparent volume of distribution.

To investigate the effects of IFB-088 on potential biomarkers.	
 Change in TDP-43 plasmatic concentration from baseline to 6 months, compared to placebo, Change in neurofilament (NfL) light chain and NfL heavy chain plasmatic concentration from baseline to 6 months, compared to placebo, Change in plasmatic (neuro)inflammatory biomarkers from baseline to 3 months, and from baseline to 6 months, compared to placebo, Change in plasmatic oxidative stress biomarkers from baseline to 3 months and from baseline to 6 months, compared to placebo.
To investigate the QoL of ALS patients.	Change in ALS assessment questionnaire (ALSAQ-40) from baseline to 6 months.

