5.2.15 Treatment emergent adverse event

TEAE is defined as an adverse event occurring (or existing symptoms worsened) on or after the day of first dose intake of study product and up to study end.

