5.2.18 Serious adverse event

SAE corresponds to AE considered as serious or AE with a missing or unknown seriousness. Seriousness of AE will be analyzed according to the investigator judgement.

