5.12.1 Adverse Events

Adverse events will be coded by Primary System Organ Class (SOC) and Preferred Term (PT) using MedDRA dictionary.

5.12.1.1 *Summary of treatment emergent adverse events*

A summary of the number of treatment emergent adverse events, number and percentage of patients with at least one AE will be presented, including:

- AE

STATISTICAL ANALYSIS PLAN		
InFlectis BioScience	Sponsor:	InFlectis BioScience
	Protocol Number:	P288ALS
VERSION 1.0 NOV 12, 2024		

- TEAE
- TEAE related to study drug
- Serious TEAE
- Serious TEAE related to study drug

- Fatal TEAE
- Fatal TEAE related to study drug

- Grade 1 (mild) TEAE
- Grade 2 (moderate) TEAE
- Grade ≥ 3 (severe) TEAE

- Grade ≥ 3 TEAE related to study drug
- Grade ≥ 3 and serious TEAE
- Grade ≥ 3 and serious TEAE related to study drug

- TEAE possibly related to Riluzole

- TEAE leading to temporary discontinuation of study drug
- TEAE leading to definitive discontinuation of study drug
- TEAE leading to premature withdrawal from the study

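### The SAP does not separate the ALS events of protocol 7.10 from other TEAEs, so the pooled TEAE rows mix disease progression with toxicity

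*Protocol*

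**What the plan says.** - **Endpoint.** Protocol section 2 gives the primary safety endpoint as "Incidence, grade and relationship to IFB-088 for treatment emergent AEs, SAEs, and AESIs", together with AEs that lead to dose interruption or discontinuation.
- **Recording.** Protocol 7.10: "Clinical events related to ALS or consisting in known ALS complications will be recorded in the AE section of the eCRF". Its list begins with "Onset, changes or aggravation of speech and/or voice disorders" and goes on to swallowing, emotional, breathing, muscle and joint, and motor-neuron signs. The only carve-out reads: "When serious, these clinical events are exempt from SAE reporting". It is lifted when the event is judged drug-related or is fatal.
- **Definition.** Protocol 7.2 treats as emergent "any event already present that worsens in either intensity or frequency following exposure to the treatments". SAP 5.2.15: "TEAE is defined as an adverse event occurring (or existing symptoms worsened) on or after the day of first dose intake". Neither has an ALS exclusion.
- **Summary.** SAP 5.12.1.1: "A summary of the number of treatment emergent adverse events, number and percentage of patients with at least one AE will be presented". The rows cover any, related, serious, fatal, graded and discontinuation-related TEAEs. None is split into ALS and non-ALS events, and SAP section 7 does not mention the matter.
- **Relationship.** SAP 5.2.16 counts *Unlikely* and missing relationship as related. Protocol 7.7, for sponsor safety reporting, groups *Unlikely* with *Not related*.
- **Seriousness.** SAP 5.2.18: "SAE corresponds to AE considered as serious or AE with a missing or unknown seriousness". It otherwise follows the investigator and does not mention the 7.10 exemption.

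**The concern.** Safety is the primary objective, and bulbar-onset ALS is expected to worsen over six months. The functions listed in 7.10 are largely those that the ALSFRS-R, MITOS and King's staging score as efficacy. If most patients in both arms have at least one ALS-progression AE, the any-TEAE row sits near its ceiling and shows little of a real toxicity difference. If the drug works, fewer ALS events in the active arm offset its toxicity in the same row.

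The grade rows are exposed too, because protocol 7.7 defines a severe AE by loss of normal daily activity, and progressing ALS produces exactly that. The related rows are partly exposed: protocol 7.7 describes *Unlikely* as fitting events better explained by the patient's clinical state, yet the SAP counts them as related.

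**Working it through.** **The plan's own figures.** Protocol 8.1.2 gives the chance of at least one SAE among 28 patients: 1 − 0.95^28 = 76.2% and 1 − 0.90^28 = 94.8%. For drop-out, 42/0.85 = 49.4, rounded up to 50. All three reproduce, and this point does not affect them.

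**Model.** Let q be the probability of at least one 7.10 event and t the probability of at least one other TEAE, assumed independent. Then P(any TEAE) = 1 − (1 − q)(1 − t). With equal q in both arms, the pooled difference is (1 − q) × (t active − t placebo). The documents give neither q nor t, so both are assumptions.

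**Dilution.** t = 30% active vs 10% placebo, with 28 and 14 evaluable patients. The last column is an exact double-binomial sum.

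| q, both arms | Placebo any TEAE | Active any TEAE | Difference | P(observed active ≤ placebo) |
|---|---|---|---|---|
| 0 (ALS events removed) | 10.0% | 30.0% | 20 points | 6.5% |
| 45% | 50.5% | 61.5% | 11 points | 29% |
| 60% | 64.0% | 72.0% | 8 points | 35% |
| 80% | 82.0% | 86.0% | 4 points | 44% |
| 95% | 95.5% | 96.5% | 1 point | 62% |

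With t = 50% vs 20%, a 30-point difference becomes 16.5, 12.0, 6.0 and 1.5 points at the same four values of q.

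**Plausible q.** Protocol 4.2.2.1 cites a loss of about one ALSFRS-R point a month in untreated patients. Exclusion criterion 7 removes patients with a pre-study decline of 0.1 or less, or 1.2 or more, points a month. If lost points follow a Poisson process, P(at least one in six months) = 1 − exp(−6r). This gives 45% at r = 0.1, 95% at 0.5 and 99.8% at 1.0. Not every lost point need be entered as an AE, so q may be lower.

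**Reversal.** For t = 30% vs 10%, the pooled rates are equal when 1 − q(active) = (1 − q(placebo)) × 0.9/0.7. Active q must then be lower by 11.4 points if placebo q is 60%, by 5.7 if 80% and by 1.4 if 95%. With Poisson events, 1 − q = exp(−λ), so λ must fall by ln(0.9/0.7) = 0.251. Placebo λ is 0.916, 1.609 and 2.996 in the three cases, so the relative cut in ALS events needed for a tie is 27%, 16% and 8%.

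A tie is easier to reach than a large reversal:
- At placebo q of 80%, a 20% cut gives 1 − q(active) = 0.2^0.8 = 0.276. The pooled active rate is 1 − 0.276 × 0.7 = 80.7%, against 82.0% on placebo.
- An apparent 10-point advantage (72.0% vs 82.0%) needs q of 60% vs 80%, which is a cut of (1.609 − 0.916)/1.609 = 43%.

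**The case against.** The strongest reply is that pooled rows are only one part of the safety evidence. The endpoint also covers grade, relationship, AESIs and discontinuations. An ALS event enters a related, serious, graded or discontinuation row only if it has that attribute, and *Not related* events stay out of the study-drug-related rows. The three AESIs (renal toxicity, symptomatic hypotension, hypertriglyceridaemia) do not overlap the 7.10 list. SAP 5.12.1.2 adds a table by SOC and preferred term, and listings of related, serious, severe and special-interest events. Laboratory, vital-sign and ECG data are analysed separately. A specific toxicity can be seen there whatever the any-TEAE rate. All of this stands. One limit is that the SOC/PT table is planned for all TEAEs only; the related, serious and grade ≥3 rows are backed by listings, which would have to be sorted by hand after unblinding.

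The inputs are also open to challenge. The one-point rate is for untreated patients, whereas everyone here takes riluzole. Protocol 7.1 asks for clinically relevant worsening of a pre-existing condition, which is stricter than one lost point. That stands too, and it is why the results are shown as a range.

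A reader might infer that the serious rows are unstable, because exempt events could count or not depending on whether the site filled in the box. The documents do not support this. Protocol 7.10 exempts these events from SAE reporting, not from assessment. Protocol 7.7 requires seriousness to be assessed for every AE, and protocol 13.2 queries missing values. The missing-as-serious default is a fallback for blanks that remain.

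Finally, removing ALS-type events could remove real toxicity. Dyspnoea is on the 7.10 list and also appears, as a possible sign of interstitial lung disease, among the discontinuation criteria in protocol 5.3. That is a fair objection to a careless split, and the fix allows for it.

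**Conclusion.** The point holds in limited form. No rule removes or separates the 7.10 events, so the pooled any-TEAE, grade, serious and withdrawal rows mix progression with toxicity. Under independence and an assumed 30% vs 10% difference in other TEAEs, a true 20 points shows as 11, 4 or 1 at an ALS background of 45%, 80% or 95%. Reversal further requires that IFB-088 lowers the ALS event rate, which is the trial's own efficacy hypothesis but is not established.

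A reader might go further and conclude that every TEAE row is dominated by progression, or that the primary endpoint cannot be read as safety. The documents do not support either: the background rate is not given, entry to a row depends on the event's attributes, and several safety outputs are unaffected. Safety is descriptive (protocol 8.1.5.1), so no test or power figure is at stake. What suffers is the reading of the pooled rows. The change is worth making because it is cheap and must be made before unblinding to be credible.

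**What to change.** In SAP 5.12.1.1:

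1. Flag the protocol 7.10 events by a preferred-term list fixed at the blinded data review.
2. Keep all the existing all-TEAE rows. Add, by arm, the same rows excluding flagged events, and one row for the flagged events themselves.
3. For this split, leave events that the investigator judges possibly, probably or definitely related in the non-ALS rows, so that possible toxicity such as dyspnoea is not removed.
4. State that serious 7.10 events count as Serious TEAE by investigator judgement, even when exempt from SAE reporting.
5. Reconcile SAP 5.2.16, which counts *Unlikely* as related, with the grouping in protocol 7.7.

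No new rule for blank seriousness boxes is needed, since protocol 13.2 already has missing values queried.

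The cost is SAP wording, one flag on the AE dataset and a second set of rows. The downside is that a few ambiguous terms, such as dyspnoea or joint pain, need a blinded judgement. Because the all-TEAE rows remain, nothing is hidden by that choice.
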